4.1 Inclusion Criteria

4.1.1 Recurrent or progressive advanced stage non-small cell lung cancer (no small cell component) with most recent treatment being an FDA approved immune checkpoint inhibitor (pembrolizumab, atezolizumab, or nivolumab)

NOTE: Pathology reports documenting the diagnosis of NSCLC are required to be reviewed to confirm outside diagnosis

4.1.2 Sufficient tumor tissue available from original diagnosis or subsequent biopsy for analysis of estrogen receptor and aromatase – tumor block or a minimum of 5 unstained slides

4.1.3 Failed at least 1 prior FDA approved treatment for advanced NSCLC. Patients with EGFR/ALK/ROS1 rearrangements should have received an FDA-approved TKI prior to enrollment on this trial.

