Treatment Plan	
Eligible, consenting patients will take exemestane 25 mg once daily by mouth after a meal for a minimum of 6 weeks (2 treatment courses) while continuing on treatment with an FDA-approved anti-PD1 or anti-PD1 antibody. A disease re-evaluation will be performed at 6 weeks and those experiencing a complete response (CR), partial response (PR) or stable disease (SD) based on the Response Evaluation Criteria in Solid Tumors (RECIST) may continue exemestane daily with standard of care ICB until disease progression, unacceptable side effects, or patient refusal/non-compliance. Patients are seen in clinic every 3 weeks with a disease re-evaluation every 6 weeks.
 
An end of treatment visit occurs 4 weeks after the last dose of exemestane or the start of a new therapy, whichever is earlier. All patients are followed for response until disease progression or the start of a new treatment, then for survival through 1 year from study enrollment.

Key Inclusion Criteria	
Advanced stage non-small cell lung cancer (NSCLC) currently receiving an FDA approved anti-PD1 or anti-PDL1 therapy with progressive diseaseSufficient tumor tissue from the diagnostic or subsequent biopsy either as a block or a minimum of 5 slides for estrogen receptor and aromatase analysisFailed at least 1 prior FDA approved treatment regimen for advanced NSCLC - Patients with EGFR/ALK/ROS1 rearrangements should have received an FDA-approved TKI prior to enrollment on this trial.Measureable disease per RECISTPost-menopausal defined as 1 year or more of amenorrhea and if < 55 years of age estradiol assay < 20 pg/mLECOG performance status 0, 1, or 2
Key Exclusion Criteria	
Untreated or unstable CNS diseaseInability or unwillingness to swallow tabletsCurrently using hormone replacement therapy (oral or patch) or/and phytoestrogen supplements (i.e. black cohosh)
Enrollment:	Stage 1: 10 patients, Stage 2 if activated, 19 additional patients

Treatment Schema

* or unacceptable toxicity, patient refusal/noncompliance/> 3 week break from therapy, or, in the opinion of the treating physician stopping therapy is in the best interest of the patient

- Clinic visit every 3 weeks during treatment
- Maintain SOC ICB specific dosing schedule
- Disease reassessment every 6 weeks during exemestane treatment

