5.2 Study Enrollment with the Masonic Cancer Center Clinical Trials Office

To be eligible for study enrollment, the patient must sign the treatment consent and meet each of the inclusion criteria and none of the exclusion on the eligibility checklist based on the eligibility assessment documented in the patient's medical record.

The Study Coordinator or designee will assign the study treatment arm to complete enrollment.

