13.1 Study Design, Objectives and Endpoints

The goal of this phase II study is to estimate the probability of response after treatment of exemestane in post-menopausal women with advanced non-small cell lung cancer progressing while on immune checkpoint blockade. The primary endpoint of treatment response will be assessed at 6 weeks after the start of treatment using RECIST criteria. Secondary endpoints include the proportion of toxicities through 30 days after the last dose or start of new treatment as described in Section 10.2.2, disease-control as measured by response duration, progression-free and overall survival through 12 months from study enrollment and quality of life scores as measured by PROMIS-29 at baseline, every 3 weeks during treatment and at the end of treatment visit. The primary endpoint of response will be evaluated using a two-stage design.

Stage 1 will enroll 10 patients. If 2 or more patients have an objective response after completion of stage 1, an additional 19 patients will be enrolled in stage 2 for a total of 29 patients. If the total number of patients responding is 4 or greater, the treatment will be considered worthy of further investigation.

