13.2 Sample Size

Sample size is based on testing our primary endpoint using Simon's optimal two stage design with a type I error of 5% and power of 80%.³⁰ Our null hypothesis is that the response is $\leq 5\%$ (as all will be progressing on anti-PD1 therapy) and our alternative hypothesis is that response is $\geq 20\%$. If the treatment is truly not effective, there is a 5% chance of concluding that the drug is effective while if the treatment is truly effective, there is a 20% chance of concluding that it is not effective. Up to 10 patients will be enrolled per year.

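### Inclusion criterion 4.1.1 is looser than the population on which the 5% null rests: read literally, it admits patients who are not on a checkpoint inhibitor and did not progress on one

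*Combined protocol and SAP*

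**What the plan says.** Section 4.1.1 admits recurrent or progressive advanced NSCLC "with most recent treatment being an FDA approved immune checkpoint inhibitor" (pembrolizumab, atezolizumab or nivolumab). It does not mention being on the drug at entry or progressing while on it.

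Other sections are narrower. The synopsis lists as a key inclusion criterion NSCLC "currently receiving an FDA approved anti-PD1 or anti-PDL1 therapy with progressive" disease, and its design paragraph speaks of women progressing during treatment. The primary objective (1.1), Section 3 and Section 13.1 do the same. Section 13.2 sets the null response rate at 5% or less, with the reason given in parentheses: "as all will be progressing on anti-PD1 therapy".

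Section 6.2 has all patients continue their prior anti-PD1 or anti-PDL1 antibody as standard of care. Under Section 5.2, a patient who signs consent is eligible for enrollment if she is found to "meet each of the inclusion criteria and none of the exclusion on the eligibility checklist".

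**The concern.** A woman who failed chemotherapy, then received a checkpoint inhibitor, stopped it without progressing and recurred later would satisfy 4.1.1 as worded. No other criterion excludes her:

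- 4.1.3 asks for failure of at least one approved treatment, and the earlier chemotherapy meets that.
- 4.1.10 sets minimum intervals after radiation, chemotherapy or experimental therapy, and surgery, but says nothing about time since the inhibitor.
- 4.2.2 and 4.2.3 concern immune-related toxicity and steroid use only.

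If she then takes the antibody again together with exemestane, a response cannot be assigned to either drug. The trial has one arm, and response at 6 weeks is the only decision endpoint. Section 13 has no rule to separate such patients. At stake is whether 4 responses in 29 still count as evidence against a 5% rate that presumes the inhibitor has already failed in everyone.

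**Working it through.** **Inputs from the documents.** Null 5%, alternative 20%, type I error 5%, power 80%, Simon's optimal design (13.2). The Stage 1 size is 10, and the continuation rule reads: "If 2 or more patients have an objective response after completion of stage 1, an additional 19 patients will be enrolled in stage 2" (13.1). Success is 4 or more responses in 29 (13.1). The response rate to checkpoint inhibitors in unselected patients is about 20-30% (2.4).

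**Inputs the documents do not give (assumptions).** The share *f* of enrolled patients who are off the inhibitor, and their response rate *q* when exemestane does nothing. I vary *f* from 10% to 30% and *q* from 5% to 30%. The upper end of *q* borrows the unselected-patient figure, so it is a bound and not an estimate.

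**Step 1: the plan's own figures.** The probability of declaring success at true rate *p* is

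P(success) = Σ over x₁ ≥ 2 of b(10, x₁, p) × P[Bin(19, p) ≥ 4 − x₁].

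At p = 0.05:

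- x₁ = 2: 0.0746 × 0.2453 = 0.0183
- x₁ = 3: 0.0105 × 0.6226 = 0.0065
- x₁ ≥ 4: 0.0010
- Total: 0.0259, or 2.6%

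At p = 0.20 the same sum gives 59.6%. The stated 5% and 80% are therefore not reproduced under the written Stage 1 rule. An exhaustive search returns Simon's optimal design as 10 then 29 patients, continuing on at least 1 response, with type I error 4.7% and power 80.1%. That mismatch in the Stage 1 threshold is a separate problem. The results below use the rule as written.

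**Step 2: null rate in a mixed population.** If patients progressing on the inhibitor respond at 5%,

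p = 0.05 + f × (q − 0.05).

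| Share *f* | Rate *q* | Null rate *p* | Type I error, written rule |
|---|---|---|---|
| any | 5% | 5.0% | 2.6% |
| 20% | 10% | 6.0% | 4.5% |
| 10% | 20% | 6.5% | 5.7% |
| 20% | 20% | 8.0% | 10.0% |
| 30% | 30% | 12.5% | 28.3% |

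For example, f = 20% and q = 20% give 0.05 + 0.20 × 0.15 = 0.08.

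**Step 3: when is 5% passed?** Setting P(success) = 0.05 under the written rule gives p = 6.2%. The share needed is (0.0622 − 0.05)/(q − 0.05):

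- q = 10%: 0.0122/0.05, about 24%
- q = 20%: 0.0122/0.15, about 8%
- q = 30%: 0.0122/0.25, about 5%

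**Step 4: small numbers.** One such patient in 29 at q = 20% gives p = 0.05 + 0.15/29 = 5.5% and a type I error of 3.5%. Two give p = 0.05 + 0.30/29 = 6.0% and 4.6%. Both stay below 5%.

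**The case against.** The strongest reply is that the plan never sets out to enroll patients who are off the inhibitor. Every other description of the population is narrower. Section 6.2 speaks of continuing the antibody, charged as before enrollment, and the schedule heads that row as continuation of standard of care. The words recurrent or progressive may describe the disease and not a treatment gap. Section 4.1.3 also helps in part: a patient whose only treatment for advanced disease was the inhibitor must have failed it. All of this stands. It makes the point an internal contradiction and not a deliberate design choice. It does not close the gap for patients who qualify through earlier chemotherapy.

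The eligibility checklist named in 5.2 is not in the documents. Whether it follows 4.1.1 or the synopsis cannot be seen, so actual enrollment of such patients is an inference.

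The assumed rates are also open to challenge. The 20-30% figure is for unselected patients, not for resuming an agent already used, and 2.4 adds that the vast majority of responders eventually become resistant. The null is stated as 5% or less. If patients progressing on the inhibitor respond at only 2% (assumption), a 20% share at a 20% rate gives p = 0.8 × 0.02 + 0.2 × 0.20 = 5.6% and a type I error of 3.7%, still under 5%.

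A reader might infer that false positives are certain to rise, or might quote figures as high as 44%. The documents support neither. A rise requires that such patients are enrolled, resume the inhibitor and respond above 5% by 6 weeks, and none of these is quantified. The 44% comes from the most extreme mixture in the table combined with continuing on at least 1 of 10, a Stage 1 rule the protocol does not contain.

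**Conclusion.** The contradiction is real. Criterion 4.1.1 is looser than the population in the synopsis, 1.1, Section 3, 13.1 and 13.2, and the only stated basis for the 5% null holds for the narrower population alone.

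The effect on error rates is conditional. It ranges from no change, if these patients respond at 5%, to a type I error of 28%, which is an upper bound. Moderate assumptions give values from just under the nominal level to about twice it. These figures rest on an assumed share and response rate, on a 5% rate in patients progressing on the inhibitor, and on the Stage 1 rule as written. The margin between 2.6% and 5% should not be relied on as protection: it comes from a Stage 1 threshold that also lowers power to 59.6%. If that threshold became at least 1 of 10, the 5% level would be passed at a null rate of about 5.1%.

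The plan should be corrected because interpretation of a positive single-arm result depends on it.

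**What to change.** Reconcile 4.1.1 with the population in the synopsis, Section 3 and 13.2: currently receiving pembrolizumab, atezolizumab or nivolumab, with progression documented while on that agent. Check that the eligibility checklist carries the same wording. The stated reason for the 5% null then applies to every enrolled patient.

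The cost is a one-line amendment and a checklist update. A few patients become ineligible, all of them outside the stated target population. Sample size and decision rules are unaffected by this change.

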4.1.4 Measureable disease by RECIST version 1.1 (Appendix II)

4.1.5 Post-menopausal defined as

- Age \geq 55 years and 1 year or more of amenorrhea
- Age $<$ 55 years and 1 year or more of amenorrhea with an estradiol assay $<$ 20 pg/mL
- Surgical menopause with bilateral oophorectomy

4.1.6 ECOG performance status 0, 1 or 2 (Appendix I)

4.1.7 Life expectancy of 3 months or more in the opinion of the enrolling investigator and documented in the medical record

4.1.8 Adequate organ function within 14 days of study enrollment defined as:

Hematology:

Absolute neutrophil count (ANC) \geq 1500/mm³, Platelets \geq 100,000/mm³, Hemoglobin \geq 8 g/dL

Biochemistry:

Total Bilirubin within normal institutional limits

AST/SGOT and ALT/SGPT \leq 2.5 x upper limit of normal (ULN), except if there is known hepatic metastasis, wherein transaminases may be \leq 5 x institutional ULN.

Serum creatinine \leq 1.5 mg/dl or glomerular filtration rate $>$ 50 ml/min

4.1.9 Must have recovered to CTCAE v 4 Grade 1 or better from the acute effects of any prior surgery, chemotherapy or radiation therapy. Chronic residual toxicity (i.e. peripheral neuropathy) is permitted

4.1.10 A minimum time period must elapse between the end of a previous treatment and start of study therapy:

- 1 week from the completion of radiation therapy for brain metastases
- 4 weeks from the completion of chemotherapy or any experimental therapy
- 4 weeks from prior major surgery (such as open biopsy or significant traumatic injury)

4.1.11 Voluntary written consent before any research related procedures or therapy

4.2 Exclusion Criteria

- 4.2.1 Known active CNS disease - If patient has history of brain metastases, the brain lesions must have been treated with radiation and/or surgery - patients should be neurologically stable and requiring ≤ 10 mg oral prednisone equivalence of steroids per day
- 4.2.2 Any toxicity from immune-related toxicity from prior immune therapy that would preclude further treatment with anti-PD-1/PDL-1 inhibitor or ongoing IR toxicity \geq Grade 2
- 4.2.3 Requiring > 10 mg prednisone equivalence of steroids per day for immune-related toxicity
- 4.2.4 Inability or unwilling to swallow study drug
- 4.2.5 Any gastrointestinal condition causing malabsorption or obstruction (eg, celiac sprue, gastric bypass surgery, strictures, adhesions, history of small bowel resection, blind loop syndrome)
- 4.2.6 Currently using hormone replacement therapy (oral or patch) or/and phytoestrogen supplements (i.e. black cohosh)
- 4.2.7 Known hypersensitivity to exemestane or its excipients
- 4.2.8 Any serious underlying medical condition that, in the opinion of the enrolling physician, would impair the ability of the patient to receive protocol treatment
- 4.2.9 Prior malignancy, with the exception of curatively treated squamous cell or basal carcinoma of the skin or in situ cervical cancer, unless there is a 3-year disease-free interval
- 4.2.10 Concomitant use of strong CYP3A4 inducers such as rifampicin, phenytoin, carbamazepine, phenobarbital, or St. John's wort as these may significantly reduce the availability of exemestane

5 Patient Registration and Study Enrollment

Written consent must be obtained prior to the performance of any research related tests or procedures. Consent is usually obtained before final eligibility is determined.

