2.5 Rationale

While modest improvements have been made in survival and quality of life in patients with advanced non-small cell lung cancer (NSCLC) there is a need to explore new agents and combinations with novel mechanisms of action in an effort to improve clinical outcomes in this patient population. With the introduction of immune checkpoint blockade and the durability of response, the vast majority of patients with NSCLC are receiving immune checkpoint blockade at some point in their therapy. However, response rate is relatively low spawning interest in developing novel combination therapies that can improve upon the response or generate responses in patients who are failing therapy. It is generally accepted that the aromatase inhibitor (AI) exemestane is less toxic than chemotherapy, yet potentially it can provide equal or greater benefit. In hormone receptor positive breast cancer, anti-estrogen therapy is a first-line treatment for metastatic disease,

and is given as adjuvant therapy for 5 years in earlier stage disease. Exemestane has been used in tens of thousands of women and its efficacy and side effect profile has been well established. Furthermore, preclinical and clinical data suggest that there might be a role of estrogen receptor signaling in maintaining immune suppression in the tumor microenvironment. Therefore, we propose a 2-stage phase II trial of exemestane in previously treated postmenopausal women with metastatic NSCLC who are progressing on anti-PD1 or anti-PDL1 therapy to determine if aromatase inhibition will result in treatment responses in this patient population and to determine whether ER-related biomarkers can identify patients likely to receive clinical benefit.

The estrogen pathway inhibition is a promising novel target in NSCLC. Preclinical evidence support targeting the synthesis of estrogen in NSCLC as a strategy that may result in enhanced antitumor activity.

3 Study Design

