6.3 Supportive Care and Prohibited Medications

Commercially available palliative and supportive care for disease-related symptoms should be offered to all treated patients.

Patients with pre-existing osteoporosis should be on treatment with calcium/vitamin D and/or bisphosphonates.

Patients must be instructed not to take any additional medications (including over-the-counter products) during the study without prior consultation with her study doctor. Use of estrogens (i.e. hormone replacement therapy) and phytoestrogen supplements (i.e. black cohosh) are prohibited during exemestane treatment.

Concomitant use of strong CYP 3A4 inducers decreases exemestane exposure therefore their use will be prohibited. For a list of CYP34A inducers refer to Appendix III.

No chemotherapy, hormonal anticancer therapy, or experimental anticancer medications other than those study related will be permitted while the patient is on study. Any disease progression requiring other forms of specific anti-tumor therapy will be cause for discontinuation from the study.

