9.2 Research Related Tests and Procedures

The PROMIS-29 Profile (Appendix VI) will be completed before starting exemestane, every 3 weeks while taking the study drug, and at the end of treatment visit.

Correlative studies will examine biomarkers in the Estrogen Receptor (ER) pathway including circulating levels of hormones and products of ER response genes. DNA will be extracted from blood collected at baseline, during treatment, and at progression and sent for sequencing using the Guardant360 assay to determine if mutations are present that are correlated with resistance to an aromatase inhibitor. Three hundred sixty (360) common mutations will be analyzed that have been used to monitor breast cancer patients on aromatase inhibitor therapy. Additionally, since cigarette smoking is associated with increased ER expression²⁹, we will measure serum cotinine in patients at baseline as a measure of recent tobacco smoke exposure.

Tumor tissue will be analyzed ER β receptor expression and aromatase at baseline using immunohistochemistry (IHC). Additionally, we will analyze PDL-1 expression if not already done for clinical reasons. Finally, we will evaluate tumor sections for CD8 T cell staining and MDSC on archival tissue as well as any post-treatment tissue obtained.

Finally, peripheral blood mononuclear cells (PBMCs) will be obtained at baseline and prior to Cycle 2 and 3 to evaluate the peripheral immunophenotype prior to and after initiation of exemestane.

10 Adverse Event Monitoring, Recording and Reporting

Toxicity and adverse events will be classified according to NCI's Common Terminology Criteria for Adverse Events V 4.0 (CTCAE).

A copy of the CTCAE can be downloaded from the CTEP home page <http://evs.nci.nih.gov/ftp1/CTCAE/About.html>

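### Section 4 does not exclude women already taking an aromatase inhibitor for earlier breast cancer, who can say little about adding one to checkpoint blockade

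*Combined protocol and SAP*

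**What the plan says.** Under 5.2 a patient is eligible if she meets every inclusion criterion and no exclusion criterion. The parts that bear on earlier hormonal treatment are these:

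- **4.2.9** excludes prior malignancy, apart from curatively treated skin cancers and "in situ cervical cancer, unless there is a 3-year disease-free interval". Breast cancer is not singled out.
- **4.2.6** is the only hormone-related exclusion: "Currently using hormone replacement therapy (oral or patch) or/and phytoestrogen supplements (i.e. black cohosh". It does not mention aromatase inhibitors, tamoxifen or fulvestrant.
- **4.1.10** sets waiting periods after brain radiation, chemotherapy or experimental therapy, and major surgery. It sets none after endocrine therapy.
- **2.5** says of anti-estrogen therapy in breast cancer that it is a first-line treatment in metastatic disease "and is given as adjuvant therapy for 5 years in earlier stage disease". Sections 2.3 and 7 describe two to three years of tamoxifen followed by exemestane to complete five years.
- **6.3** states: "No chemotherapy, hormonal anticancer therapy, or experimental anticancer medications other than those study related will be permitted while the patient is on study".
- **9.1** records concomitant medication and previous cancer treatment at baseline. **13.3** plans no analysis or description by earlier endocrine exposure.

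**The concern.** The rationale in 2.5 asks whether aromatase inhibition produces responses in women who are progressing on checkpoint blockade. That presupposes that aromatase inhibition is new to the patient at entry. If she was already taking an aromatase inhibitor while her lung cancer progressed, she has in effect failed the combination already, and exemestane continues or replaces a drug of the same class. She still counts in the 10 and the 29.

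Two things are at stake. The first is dilution of the response rate in a small trial with an early futility look. The second is the correlative work in 9.2. Circulating hormones would already be suppressed at baseline. The sequencing is meant "to determine if mutations are present that are correlated with resistance to an aromatase inhibitor", and such mutations could date from her breast cancer treatment. The blood-cell comparison before and after starting exemestane would have no untreated starting point.

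**Working it through.** **Step 1: can such a woman pass Section 4?** Take adjuvant therapy of 5 years (2.5) and a required disease-free interval of 3 years (4.2.9), and assume both clocks start at about the same time. That leaves 5 − 3 = 2 years in which she is eligible under 4.2.9 and still on adjuvant treatment. Neither 4.2.6 nor 4.1.10 stops her. On the sequence in 2.3 and 7, she could already be taking exemestane itself.

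**Step 2: does 6.3 close the gap?** No. It governs treatment on study and is not an entry criterion. It cannot undo exposure during the checkpoint inhibitor treatment that failed. Section 4 admits her on a drug that 6.3 then bars, and nothing says how the two fit together.

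**Step 3: reproduce the plan's design.** Section 13.2 specifies "Simon's optimal two stage design with a type I error of 5% and power of 80", with a null response of 5% and an alternative of 20%. Section 13.1 gives n1 = 10, n2 = 19 and final success at 4 or more of 29. With c1 the number of Stage 1 responses needed to continue,

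P(success) = Σ from x = c1 to 10 of P(X1 = x) × P(X2 ≥ 4 − x), where X1 ~ Bin(10, p) and X2 ~ Bin(19, p).

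At p = 0.20:

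| x in Stage 1 | P(X1 = x) | P(X2 ≥ 4 − x) | Product |
|---|---|---|---|
| 1 | 0.2684 | 0.7631 | 0.2048 |
| 2 | 0.3020 | 0.9171 | 0.2770 |
| 3 | 0.2013 | 0.9856 | 0.1984 |
| 4 or more | 0.1209 | 1 | 0.1209 |

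- Printed rule (c1 = 2): 0.2770 + 0.1984 + 0.1209 = 0.596. Type I error at p = 0.05 is 0.026.
- c1 = 1: 0.596 + 0.205 = 0.801. Type I error is 0.047.

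The stated 80% power and 5% error therefore match a 1-of-10 Stage 1 rule, not the printed 2-of-10 rule. That mismatch is a separate and larger point, so both rules are carried below.

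**Step 4: dilution.** Assumptions, none of them in the documents as expectations: a share f of patients is already on an aromatase inhibitor, they respond at 5% (the plan's null rate), and everyone else responds at 20%. Then p = 0.20(1 − f) + 0.05f.

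| f | Expected number of 29 | p | Power, printed rule | Power, 1-of-10 rule |
|---|---|---|---|---|
| 0 | 0 | 0.2000 | 59.6% | 80.1% |
| 3% | 0.87 | 0.1955 | 58.0% | 78.7% |
| 5% | 1.45 | 0.1925 | 56.9% | 77.6% |
| 10% | 2.9 | 0.1850 | 54.1% | 74.9% |

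If exposed women respond at 0% instead, the figures are 57.5% and 78.2% at f = 3%, and 52.1% and 73.0% at f = 10%.

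**Step 5: Stage 1 alone.** With one exposed woman among the first 10:

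- P(0 responses) = 0.95 × 0.8⁹ = 0.1275
- P(1 response) = 0.05 × 0.8⁹ + 0.95 × 9 × 0.2 × 0.8⁸ = 0.2936

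The chance of passing the printed rule is 1 − 0.1275 − 0.2936 = 57.9%, against 62.4% with none. One in ten is already the top of the assumed range. At f = 3%, the chance that Stage 1 holds no such woman is 0.97¹⁰ = 74%.

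**Step 6: direction.** If exposed women respond at 5% or less, the overall rate under the null is at most 5%, so type I error does not rise.

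**The case against.** The strongest case against acting is rarity. A patient must have had endocrine-treated breast cancer, be three years disease-free, still be on an aromatase inhibitor, and have lung cancer progressing on a checkpoint inhibitor. The documents give no frequency, and the number enrolled may be zero. At the low end of the assumed range the power loss is about 1.5 points. Baseline records would identify any such woman, 6.3 stops her taking a second agent on study, and the correlative aims are exploratory. All of this stands and limits the weight of the point. It does not close the gap: recording exposure does not keep the patient out of the response count, and 13.3 plans no use of the record.

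A reader might infer more than the documents support:

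- **That the same holds for tamoxifen or fulvestrant.** Section 2.2 separates drugs that block the receptor from drugs that inhibit estrogen production and treats the latter as more effective in breast cancer. Sections 2.3 and 7 give an exemestane indication for disease that progressed after tamoxifen. In these women exemestane does add aromatase inhibition.
- **That a woman under 55 could qualify as post-menopausal only because her drug lowers estradiol.** Criterion 4.1.5 also requires at least a year of amenorrhea, so a low assay alone admits nobody.
- **That the gap could produce a false positive.** Step 6 shows the bias runs the other way if exposed women respond at 5% or less.
- **That the route wording in 4.2.6 is part of this.** It is a separate minor matter.

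**Conclusion.** The gap is real for women whose aromatase inhibitor use is current or overlapped the failing checkpoint inhibitor. They can be enrolled and counted, yet they contribute little to the add-on question, and their baseline hormone, mutation and immune samples are not untreated baselines. With an assumed exposed share of 3% to 10% and a 5% response in those women, power drops by 1.6 to 5.5 points under the printed rules (59.6% to 58.0–54.1%) and by 1.4 to 5.2 points with a 1-of-10 Stage 1 rule (80.1% to 78.7–74.9%). The share and the response rate are both assumptions. The error is toward missing an effect. This is a cheap improvement that protects the trial's own question, not a defect that undermines the design. Section 4 and 6.3 should also be reconciled, because one admits a patient on a drug that the other bars.

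**What to change.** Add one exclusion to 4.2: aromatase inhibitor use that is current, or that occurred during the checkpoint inhibitor treatment on which the patient is progressing. Use the existing baseline row in 9.1 for previous cancer treatment to record any other earlier hormonal anticancer therapy, and have 13.3 say that it will be described. State how Section 4 and 6.3 fit together for a woman who enters on another hormonal anticancer drug; how that is handled clinically is for the sponsor to settle.

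The cost is an amendment of a few lines and an eligibility checklist update. The downside is the loss of otherwise eligible patients: 29 × 0.03 = 0.9 to 29 × 0.10 = 2.9 under the assumed range, so about 0 to 3 over the trial.
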